### **8.2.2. Classic and FSHD TUG**

The TUG test, which is used to assess a person's mobility, requires dynamic balance. The TUG measures the time that a person takes to rise from a chair, walk 3 meters, turn around, walk back to the chair, and sit down. The FSHD TUG adds to the classic TUG by incorporating trunk and upper extremity components (supine to sit and sit to supine). The FSHD TUG will capture total completion time and completion times for each segment (supine to sit, sit-to-stand then walk-and return to-sit, and sit to supine). Each test is done

twice per visit. Schedule of classic and FSHD TUG assessments are described in [Appendix 14.2](#). The average of Trial 1 and Trial 2 assessments at each visit will be derived for both the classic TUG completion time and each of the FSHD TUG completion times (ie, supine to sit, sit-to-stand then walk- and return to-sit, sit to supine, and total) and will be used for the analysis.

For each treatment sequence/entry point of OLE, descriptive statistics of classic TUG average completion time and FSHD TUG average completion times in seconds per visit as well as the change from baseline will be provided in tables. Descriptive statistics of FSHD TUG average completion times will be presented for each segment (supine to sit, sit-to-stand then walk-sit, sit to supine, and total). Similar methods will be used to analyze the change from baseline in FSHD TUG average completion times.

Similar analysis will also be conducted for each of the individual components of the FSHD TUG.

To assess the efficacy of losmapimod in the placebo group after rollover into the OLE and the durability of efficacy in the losmapimod group, the mean change from baseline (+- SE) by visit of classic TUG will be graphically presented over both the placebo-controlled treatment period and OLE.

Three types of % change/year in classic TUG will be estimated. The analysis approaches will be similar to those of the MRI longitudinal composite scores in Section 8.1.

### **8.2.3. Manual Dynamometry**

Qualitative isometric dynamometry (hand-held dynamometer) will be used to assess the skeletal muscle strength of study subjects in both the upper and lower limbs bilaterally. Shoulders, flexors and extensors in the elbow, knees, and ankles as well as the grip bilaterally will be measured at each applicable visit. Isometric dynamometry measures the static muscle strength without any movement. The schedules of manual dynamometry assessments are described in [Appendix 14.2](#).

Total dynamometry results on all muscles combined, upper extremity, lower extremity are derived; average and maximum weight in kilogram per visit are also derived for analysis. For each treatment sequence/entry point of OLE, descriptive statistics of total, average and maximum weight in kilogram per visit as well as the change from baseline and percent change from baseline will be presented overall and according to assessment (dominant shoulder abductors, non-dominant shoulder abductors, dominant elbow flexors, non-dominant elbow flexors, dominant elbow extensors, non-dominant elbow extensors, right

ankle dorsiflexors, left ankle dorsiflexors, dominant hand grip, and non-dominant hand grip). The averages from dominant and non-dominant averages and maximums on all assessments will be analyzed similarly.

Similar analysis will be done for total average manual dynamometry for: (a.) all muscles combined; (b.) upper extremity strength, in the shoulders and elbows combined; and (c.) lower extremity strength, which includes right ankle dorsiflexors, and left ankle dorsiflexors muscles combined.

To assess the efficacy of losmapimod in the placebo group after rollover into the OLE and the durability of efficacy in the losmapimod group, the mean change from baseline (+- SE) by visit of all manual dynamometry measures will be graphically presented over both the placebo-controlled treatment period and OLE.

Three types of % change/year in dynamometry results, overall and per assessment, will be estimated. The analysis approaches will be similar to those of the MRI longitudinal composite scores in Section 8.1.

#### **8.2.4. MFM Domain 1**

The MFM scale, which assesses the severity of the motor deficit, provides a clinician's assessment of functionality impairment for standing and transfers. Domain 1 has 13 items in version 1 and 15 items in version 3 of the protocol with each item scored from 0 to 3. The MFM Domain 1 score corresponds to the sum of the item scores divided by the maximum score for this dimension and multiplied by 100 (ie, sum of scores/39\*100 for 13 items questionnaire and sum of scores/45\*100 for the 15 items questionnaire). Schedule of MFM assessments are described in [Appendix 14.2](#).

For each treatment sequence/entry point of OLE, descriptive statistics of the MFM Domain 1 scores (individual item scores and Domain 1 score) per visit as well as the change from baseline will be presented.

Shift in MFM Domain 1 scores from baseline will also be presented. Baseline results will be categorized into 0 to 25, >25 to 50, >50 to 75, >75 to 100. Post baseline results will be presented as shift to high, no change, or shift to low depending on the change relative to baseline. For example, if the subject has baseline MFM Domain 1 score belonging to category >25 to 50 and the post baseline MFM Domain 1 score is 54, then, the post baseline result considered as shift to high.

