### **3. Investigational Plan**

#### **3.1. Overall Study Design and Plan**

Once subjects reach Week 48, they will have the option to roll over into the OLE, with all subjects receiving 15 mg PO losmapimod tablets BID. Subjects who wish to roll over into the OLE must complete all procedures from the Week 48 end of placebo-controlled treatment period/start of OLE visit.

Subjects will remain in the OLE until study drug approval or until the study is discontinued by the sponsor. All subjects who complete or discontinue from treatment will complete a safety follow-up visit 7 days (+/- 3 days) after the last dose of study drug.

During the OLE, subjects will attend clinic visits approximately every 12 weeks. Study drug (open-label losmapimod) will be administered BID and should be taken with food. The first dose of OLE drug will be the day after the Week 48 visit.

The OLE will evaluate the safety and tolerability of long-term dosing with losmapimod in treating subjects with FSHD1. The efficacy data will be collected until protocol version 5.0 is executed. The efficacy analysis will be conducted when available efficacy data are fully cleaned.

Prior to the COVID-19 pandemic, subjects who reached the Week 24 visit had the option to roll over into the OLE. Subjects who had already rolled over to the OLE prior to the COVID-19 pandemic will remain on open label treatment. Their next clinic visits will follow the assessments for the Week 36 and Week 48 visits in the placebo-controlled portion of the study as described in the COVID-19 Pandemic Emergency protocol version 4.0. The first dose of OLE drug for these subjects will be the day after the Week 24 visit.

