#### **4.4. Baseline, Study Day, and Change from Baseline Definitions**

Unless indicated otherwise, baseline will be defined as the last non-missing evaluation on or before the day of first dose of study drug in the placebo-controlled treatment period. If the last non-missing evaluation and the study drug administration occur on the same day, timing of the evaluation will be used to determine the pre- or post-dose. If timing is not available, the evaluation is considered pre- or post-dose based on the schedule of events for that assessment. For example, AEs and concomitant medication are considered post-baseline evaluations.

For the OLE baseline, it is defined as the last non-missing evaluation before the first dose of losmapimod in the OLE.

Relative study days will be calculated as:

$(\text{assessment date} - \text{first study drug administration date}) + 1$

if the assessment date is on the same day or after the first dosing date, otherwise:

$(\text{assessment date} - \text{first study drug administration date})$ .

Where applicable, study day relative to first dose of losmapimod will also be provided and this will be calculated as:

$(\text{assessment date} - \text{first losmapimod administration date}) + 1$

if the assessment date is on the same day or after the first dosing date, otherwise:

$(\text{assessment date} - \text{first losmapimod administration date})$ .

Both study days will be presented on all listings where appropriate.

Change from baseline will be computed as (post-baseline assessment value - baseline assessment value). Percent change from baseline will be computed as  $(\text{change from baseline value} / \text{baseline assessment value}) * 100$ . For the OLE visits, change from baseline will be computed based on both baseline assessment value, baseline in the placebo-controlled treatment period and baseline in OLE.

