## **4.10. Analysis Set**

### **4.10.1. Open-label Analysis Set**

The open-label analysis set will consist of all subjects who complete 24 or 48 weeks of treatment in the placebo-controlled treatment period and receive at least 1 dose of open-label losmapimod in the OLE.

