14.2.4.3.4.1	Table 14.2.4.3.4.1 Annualized Change in Dynamometry Results through RCT+OLE Data-Cut Date (ddmmmyyyy) Open-label Analysis Set	Open-label Analysis Set	R	8.2.3	Efficacy	
14.2.4.3.4.2	Table 14.2.4.3.4.2 Annualized Change in Dynamometry Results in RCT Period Open-label Analysis Set	Open-label Analysis Set	R	OLE	Efficacy	
14.2.4.3.4.3	Table 14.2.4.3.4.3 Annualized Change in Dynamometry Results in OLE Period through Data-Cut Date (ddmmmyyyy) Open-label Analysis Set	Open-label Analysis Set	R	OLE	Efficacy	
14.2.4.4.1	Table 14.2.4.4.1 Shift in Motor Function Measure (MFM) Individual Component Score through Data-Cut Date (ddmmmyyyy) Open-label Analysis Set	Open-label Analysis Set	U	8.2.4	Efficacy	
14.2.4.4.2	Table 14.2.4.4.2 Change from Baseline in Motor Function Measure (MFM) Domain 1 Score through Data-Cut Date (ddmmmyyyy) Open-label Analysis Set	Open-label Analysis Set	U	8.2.4	Efficacy	
14.2.4.4.3	Table 14.2.4.4.3 Shift in Motor Function Measure (MFM) Domain 1 Score through Data-Cut Date (ddmmmyyyy) Open-label Analysis Set	Open-label Analysis Set	R	8.2.4	Efficacy	
14.2.4.5	Table 14.2.4.5 Change from Baseline in FSHD Heath Index (FSHD-HI) through Data-Cut Date (ddmmmyyyy) Open-label Analysis Set	Open-label Analysis Set	U	8.2.5	Efficacy	
14.2.4.6.1	Table 14.2.4.6.1 Patients' Global Impression of Change (PGIC) Improved and Not Improved through Data-Cut Date (ddmmmyyyy) Open-label Analysis Set	Open-label Analysis Set	U	8.2.6	Efficacy	
14.2.4.6.2	Table 14.2.4.6.2 Patients' Global Impression of Change (PGIC) through Data-Cut Date (ddmmmyyyy) Open-label Analysis Set	Open-label Analysis Set	U	8.2.6	Efficacy	

14.2.4.6.3	Table 14.2.4.6.3 Summary of Patients' Global Impression of Change (PGIC) through Data-Cut Date (ddmmmyyyy) Open-label Analysis Set	Open-label Analysis Set	U	8.2.6	Efficacy	
14.2.4.6.4	Table 14.2.4.6.4 Patients' Global Impression of Change (PGIC) Not Worsened and Worsened through Data-Cut Date (ddmmmyyyy) Open-label Analysis Set	Open-label Analysis Set	R	8.2.6	Efficacy	
14.3.1.1.1	Table 14.3.1.1.1 Overall Treatment-Emergent Adverse Events through Data-Cut Date (ddmmmyyyy) Open-label Analysis Set	Open-label Analysis Set	U	9.1	Safety	Y
14.3.1.1.2	Table 14.3.1.1.2 Overall Treatment-Emergent Adverse Events During Open-label Extension through Data-Cut Date (ddmmmyyyy) Open-label Analysis Set	Open-label Analysis Set	U	9.1	Safety	Y

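### MFM Domain 1 change and shift from the original baseline do not require the same form, so a 13-item baseline compared with a 15-item visit can show the change of form as a change in function

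*SAP*

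**What the plan says.** SAP 8.2.4 recognises two forms: "Domain 1 has 13 items in version 1 and 15 items in version 3 of the protocol", "with each item scored from 0 to 3". It handles them by rescaling: "The MFM Domain 1 score corresponds to the sum of the item scores divided by the maximum score for this dimension", times 100, which is sum/39 or sum/45.

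The section then plans descriptive statistics by visit with change from baseline, and adds that "Shift in MFM Domain 1 scores from baseline will also be presented". One set of categories, cut at 25, 50 and 75, serves both forms.

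SAP 4.4 makes the last non-missing value up to first dose in the placebo-controlled period the default baseline. For OLE visits, "change from baseline will be computed based on both baseline assessment value, baseline in the placebo-controlled treatment period and baseline in OLE". Neither section sets a condition on form. Nor do the rules on missing data (4.3), visit windows (4.5) or multiple values (4.6). The planned MFM tables in SAP 14.4 are not split by form.

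Two further statements bear on scope:
- The analysis set is limited to subjects who complete 24 or 48 weeks of the placebo-controlled period and "receive at least 1 dose of open-label losmapimod in the OLE" (SAP 4.10.1).
- "The efficacy data will be collected until protocol version 5.0 is executed" (SAP 3.1), and no MFM is scheduled in the version 5.0 extension (protocol Table 3).

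**The concern.** Dividing by each form's own maximum puts both scores on 0 to 100, but a given percentage need not mean the same function on both. The two added items may be easier or harder than the other 13. A subject whose function has not changed keeps the same score across forms only if the added items score, on average, exactly what the other 13 score.

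The form is tied to protocol version, so within a subject the switch runs one way, from the shorter form to the longer one. Any artefact therefore lines up with follow-up time, which is what Tables 14.2.4.4.2 (change from baseline) and 14.2.4.4.3 (Domain 1 shift) display. Those tables could show improvement or decline, or a shift to a higher or lower category, when function is the same. Results are also split by treatment sequence and OLE entry point (SAP 4.2). Only 12 subjects rolled over at Week 24 (protocol 3.1.1), so a few mixed-form subjects could visibly move those columns.

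**Working it through.** **Inputs.** SAP 8.2.4 gives 13 and 15 items, item range 0 to 3, divisors 39 and 45, and shift cuts at 25, 50 and 75. Two assumptions are not in the documents: the 13 items are nested in the 15, and the subject's function is the same at both assessments.

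**The plan's own figures.** 13 × 3 = 39 and 15 × 3 = 45, as stated. The worked example (baseline in the >25 to 50 category, visit score 54) is a shift to high, as stated.

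**Formula.** Let S be the sum on the 13 shared items (0 to 39), the same at both times. Let x be the sum on the two added items (0 to 6), scored only at the later visit.

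Artefact = 100(S + x)/45 − 100·S/39 = 100(13x − 2S)/585

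**Range.**
- S = 39, x = 0: 100.0 to 86.7, a change of −13.3.
- S = 0, x = 6: 0.0 to 13.3, a change of +13.3.
- The artefact is zero only if x = 2S/13. Whole scores allow this at four pairs (S, x): (0,0), (13,2), (26,4) and (39,6).
- Each raw point of x away from 2S/13 moves the score by 100/45 = 2.2 points.

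**Category shifts.** All 40 × 7 = 280 combinations were enumerated and the SAP cuts applied to both scores.
- A false downward shift is possible at S = 10, 11, 20, 21, 22, 30, 31, 32 and 33 (9 sums).
- A false upward shift is possible at S = 6, 7, 8, 9, 17, 18, 19, 28 and 29 (9 sums).
- Counted as pairs, 38 of 280 (13.6%) cross a cut. The pairs are not weighted by how likely they are.

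| S | Baseline, S/39 | x | Visit, (S+x)/45 | Change | Result |
|---|---|---|---|---|---|
| 30 | 76.9 | 2 | 71.1 | −5.8 | shift to low |
| 30 | 76.9 | 3 | 73.3 | −3.6 | shift to low |
| 30 | 76.9 | 4 | 75.6 | −1.4 | no shift |
| 29 | 74.4 | 5 | 75.6 | +1.2 | shift to high |
| 33 | 84.6 | 0 | 73.3 | −11.3 | shift to low |
| 33 | 84.6 | 1 | 75.6 | −9.1 | no shift |
| 19 | 48.7 | 6 | 55.6 | +6.8 | shift to high |
| 26 | 66.7 | 0 to 6 | 57.8 to 71.1 | −8.9 to +4.4 | no shift |

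The S = 19 row makes the same category crossing as the SAP's own worked example.

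**Same-form check.** With the common items over 39 at both times, the change is 100·S/39 − 100·S/39 = 0 for every S, and no category shift occurs.

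**Do mixed pairs arise?** The tables cover only OLE entrants. Their extension visits fall under protocol version 3.0 (the 12 early rollovers) or later. The SAP nevertheless defines a 13-item score. A subject with a 13-item baseline would then have 15-item extension visits, provided version 4.0 kept the 15-item form.

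**The case against.** The strongest reply is that the SAP nowhere says any subject changed form. It also summarises placebo-controlled data, so it could need the 13-item formula even if nobody switched. The number of mixed pairs could be small or zero. That stands as a limit on size. It does not supply a same-form rule, and if the count is zero one sentence in the SAP closes the matter.

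Second, the extremes are unlikely. A change of −13.3 needs full marks on 13 items and none on the added two. Of the 38 false shifts, 13 lie at S = 6 to 11, low scores for a population that excludes wheelchair and walker users (protocol 4.1.1). If x is within one raw point of 2S/13 (82 pairs), the artefact is at most 2.2 points and only two false shifts remain: (10,1) and (29,5). This is fair, but the documents give no item difficulty from which to judge how close x will be.

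Third, safeguards are partly planned. Item scores are summarised by visit, and Table 14.2.4.4.1 is titled "Shift in Motor Function Measure (MFM) Individual Component Score through Data-Cut Date". Change from the OLE baseline is probably same-form and unaffected. These outputs could help expose an artefact, but they do not correct the Domain 1 change and shift tables.

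Fourth, the endpoint is exploratory, with no MFM model or test in this SAP. That is accepted and limits the weight of the point. The placebo-controlled SAP, the study reference manual and the table shells were not available and might contain a rule, but this SAP refers to none for MFM form.

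**Conclusion.** The concern holds, with medium confidence, and the plan should be changed. As written, the rule gives a wrong Domain 1 change for mixed-form pairs unless the added items happen to score in exact proportion to the rest. Assuming nested items and unchanged function, the error for one subject lies between −13.3 and +13.3 points, and a false category shift is possible at 18 of 40 baseline sums.

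The effect on group means cannot be sized. The documents do not give the number of mixed-form subjects, the distribution of S and x, or the form used under version 2. The net direction is unknown, and no difference between the randomized arms is expected. What is at stake is the reading of the long-term MFM course, not an inferential result.

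**What to change.** In SAP 8.2.4, for Domain 1 change and shift from the original baseline, score the items common to both forms at every visit: sum/39 × 100 if the 13 are nested in the 15. If they are not nested, restrict change and shift to same-form pairs. Report the 15-item score as observed values, or as change between two 15-item assessments such as change from the OLE baseline. State which form each protocol version used and how many subjects have mixed forms, by treatment sequence and OLE entry point.

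The cost is SAP wording and one derivation. No new data are needed, because item scores are already collected and an item-level shift table is already planned. The downside is that two items leave the change score for everyone or, under the same-form rule, mixed-form subjects leave the comparison.

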### 8.2.5. FSHD-HI

The FSHD-HI is an FSHD-specific patient-reported measure of disease burden on activities of daily living, quality of life, and symptom prevalence and severity. The measure consists of a questionnaire with 116 items developed from qualitative interviews of patients. The 14 subscales in the FSHD-HI measure patients' perception of their ambulation and mobility, hand function, shoulder and arm function, emotional health, back/chest/abdomen strength, fatigue, pain, eating function, ability to do activities, communication ability, satisfaction in social situations, performance situations, body image and cognition. The 116 items are combined into a total score; the score is then transformed onto a percentage scale, with 100 representing maximal disability, and lower scores representing decreasing disability. This FSHD-HI total score will be calculated by a separate vendor. This score, along with the 14 subscale scores, will be assessed as shown in the schedule described in [Appendix 14.2](#).

For each treatment sequence/entry point of OLE, descriptive statistics of the FSHD-HI total and subscale scores per visit as well as the change from baseline will be presented. Similar methods will be used to analyze the change from baseline in FSHD-HI subscale scores.

### 8.2.6. PGIC

[figure not shown]
The PGIC will be assessed to obtain the subject's rating of overall improvement. The rating has the following scores: 1= Very much improved, 2= Much improved, 3= Minimally improved, 4= No change, 5= Minimally worse, 6= Much worse, 7=Very much worse. The schedule of PGIC assessments is described in [Appendix 14.2](#).

Responses of 1, 2, and 3 will be considered "improved", while responses of 4, 5, 6, and 7 will be considered not improved. Alternatively, responses of 1, 2, 3 and 4 will be considered as not worsened, and responses of 5, 6 and 7 will be considered as worsened. For each treatment sequence/entry point of OLE, descriptive statistics of PGIC values and PGIC response categories will be presented.

To assess the efficacy of losmapimod in the placebo group after rollover into the OLE and the durability of efficacy in the losmapimod group, the mean (+- SE) by visit of PGIC will be graphically presented over both the placebo-controlled treatment period and OLE.

## 8.3. Inflammatory, Immune, Apoptotic, and Muscle Disease Transcripts

The analysis of these exploratory endpoints will be described in a separate document.

## 9. Safety Analysis

### 9.1. Adverse Events

A treatment-emergent AE (TEAE) is defined as an AE that meets any of the following conditions:

- begins on or after the first dose of study drug and before 8 days after the stop of study drug;
- begins before the first dose of study drug and worsens on or after the first dose of study drug and before 8 days after the stop of study drug;
- is completely missing an onset date and end date;
- is completely missing an onset date and the end date is on or after the first dose of study drug.

For the purpose of inclusion in TEAE tables, incomplete AE onset and end dates will be imputed as follows:

Missing onset dates (where UK and UKN indicate unknown or missing day and month respectively):

- UK-MMM-YYYY: If the AE month and year are different from the month and year of the first dose of study drug, assume 01-MMM-YYYY. If the month and year are the same as the first dose of study drug month and year and the AE end date (after any imputation) is on or after the first dose of study drug, then assume the date of the first dose of study drug. If the AE month and year are the same as the first dose of study drug month and year and the AE end date (after any imputation) is prior to the first dose of study drug, then assume the end date for the onset date.
- DD-UKN-YYYY/UK-UKN-YYYY: If the AE year is different from the year of first dose of study drug, assume DD-JAN-YYYY/01-JAN-YYYY of the collected year. If the AE year is the same as the first dose of study drug year and the AE end date

(after any imputation) is on or after the first dose of study drug, then assume the date of the first dose of study drug. If the year is the same as the first dose of study drug and the AE end date (after any imputation) is prior to the first dose of study drug, then assume the end date for the onset date.

Missing end dates (where UK and UKN indicate unknown or missing day and month respectively):

- UK-MMM-YYYY: Assume the last day of the month;
- DD-UKN-YYYY: Assume DD-DEC-YYYY;
- UK-UKN-YYYY: Assume 31-DEC-YYYY.

All AEs will be classified by SOC and PT according to the MedDRA version 22.0 or higher.

An overview summary of the number and percentage of subjects with any TEAE, serious TEAE, study drug-related TEAE, study drug-related serious TEAE, TEAE leading to treatment discontinuation, TEAE leading to study withdrawal, and AE leading to death throughout the duration of the study will be provided. An TEAE is considered as study drug-related if the relationship assessment provided by the investigator is “Possibly Related”, “Probably Related”, “Definitely Related”, or missing.

In addition, the number and percentage of subjects with at least one AESI will be presented. Adverse events of special interest for this study include liver tests that meet the criteria for potential drug-induced liver injury (DILI) in accordance with the US Food and Drug Administration (FDA) “Guidance for Industry-Drug-Induced Liver Injury: Premarketing Clinical Evaluation”. Further details of liver tests and criteria are described in [Section 9.2.2](#).

A separate presentation, unless otherwise specified, will be provided for TEAEs that occurred during the placebo-controlled treatment period and OLE. A total column will be presented for tables showing TEAEs during the OLE.

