## 1. Introduction

This statistical analysis plan (SAP) describes the analyses and data presentation for the Open-label extension (OLE) part of protocol FIS-002-2019 which is being conducted under the sponsorship of Fulcrum Therapeutics (Fulcrum) in accordance with applicable standard operating procedures. The efficacy analyses will be conducted at OLE visits with available subject data. Statistical analyses are being conducted under contract with █, part of Thermo Fisher Scientific, in collaboration with Fulcrum.

The Clinical, Data Management, and Biostatistics departments at █ will work diligently and collaboratively with Fulcrum to ensure that the data collected and analyzed for this study are of high quality. This will be accomplished in part by having thorough edit checks written, programmed, and updated as needed.

This SAP is based on the protocols version 4.0 (COVID-19 Pandemic Emergency Amendment) dated 10Apr2020 and version 5.0 dated 16Aug2022. This SAP contains definitions of analysis population, derived variables, and statistical methods for the analysis of the OLE and in some parts of this SAP, a combination of placebo-controlled treatment period and OLE analysis. A separate SAP was created for the placebo-controlled treatment period.

The OLE will evaluate the safety, tolerability, and efficacy of long-term dosing with losmapimod in treating subjects with Facioscapulohumeral Muscular Dystrophy type 1 (FSHD1).

The term study drug that is being used throughout this document refers to losmapimod and/or placebo.

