### 4.1. Analysis Periods

For the purposes of efficacy and safety data analysis, and for reporting, two analysis periods for post baseline data are defined: placebo-controlled treatment period and OLE. The placebo-controlled treatment period encompasses data through Week 48 or Week 24 for subjects who prior to the COVID-19 pandemic had the option to roll over into the OLE at Week 24. The OLE encompasses all losmapimod data starting a day after the Week 48 visit or Week 24 visit for subjects who prior to the COVID-19 pandemic had the option to roll over into the OLE at Week 24. The duration of OLE is defined for each subject as the time after completion of the Week 48 or Week 24 for subjects who prior to the COVID-19

pandemic had the option to roll over into the OLE at Week 24 through completion of the safety follow-up after the end of treatment or discontinuation of the study.

In addition, a supplementary analysis period will be considered which is the losmapimod exposure period that encompasses all losmapimod exposure data, irrespective of when the losmapimod exposure starts (i.e., baseline or OLE).

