#### **4.2. Treatment**

Data will be summarized according to sequence of treatment assignment and entry point of OLE:

- Placebo BID/Losmapimod 15 mg BID for subjects who completed 48 weeks of treatment in the placebo-controlled treatment period: This will include subjects who were assigned to Placebo at baseline and shifted to losmapimod 15 mg BID after Week 48 visit.
- Losmapimod 15 mg BID/Losmapimod 15 mg BID for subjects who completed 48 weeks of treatment in the placebo-controlled treatment period: This will include subjects who were assigned to losmapimod at baseline and shifted to losmapimod 15 mg BID after Week 48 visit.
- Placebo BID/Losmapimod 15 mg BID for subjects who completed 24 weeks of treatment in the placebo-controlled treatment period: This will include subjects who were assigned to Placebo at baseline and shifted to losmapimod 15 mg BID after Week 24 visit.
- Losmapimod 15 mg BID/Losmapimod 15 mg BID for subjects who completed 24 weeks of treatment in the placebo-controlled treatment period: This will include subjects who were assigned to losmapimod at baseline and shifted to losmapimod 15 mg BID after Week 24 visit.

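### The hematology and chemistry worst-value shift tables pool placebo and losmapimod results for former placebo subjects, with no losmapimod-only summary; SAP 9.1 also gives no rule for allocating partially dated AEs to a period

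*SAP*

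**What the plan says.** **Laboratory shift tables.**
- SAP 4.2 sets the columns: "Data will be summarized according to sequence of treatment assignment and entry point of OLE". A subject who took placebo and then losmapimod sits in one column throughout.
- SAP 9.2 covers both periods. SAP 9.2.1 and 9.2.2 compare baseline with the lowest and highest post-baseline results.
- SAP 14.4 lists one such table for hematology (14.3.4.1.2) and one for chemistry (14.3.4.2.2), each through data cut-off and each marked for the Safety Review Committee.
- SAP 4.4 takes baseline, by default, before the first randomized dose. It adds an OLE baseline, but calls for both baselines only for change from baseline at OLE visits, not for shifts.
- SAP 4.1 defines what is needed to separate the treatments: "a supplementary analysis period will be considered which is the losmapimod exposure period that encompasses all losmapimod exposure data". In the list of tables, only treatment duration and compliance (14.1.6.1, 14.1.6.2) carry that period in their titles.

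**Adverse events.**
- SAP 9.1 says: "A separate presentation, unless otherwise specified, will be provided for TEAEs that occurred during the placebo-controlled treatment period and OLE". SAP 14.4 has seven such pairs of tables. On the boundary, SAP 4.1 says: "The OLE encompasses all losmapimod data starting a day after the Week 48 visit or Week 24 visit".
- With the day missing, the onset rule is: "If the AE month and year are different from the month and year of the first dose of study drug, assume 01-MMM-YYYY". With the month missing: "If the AE year is different from the year of first dose of study drug, assume DD-JAN-YYYY/01-JAN-YYYY of the collected year". The remaining branches also refer to the first dose of study drug, and SAP 1 defines that term: "The term study drug that is being used throughout this document refers to losmapimod and/or placebo".
- The worsening rule covers an AE that "begins before the first dose of study drug and worsens on or after the first dose of study drug".

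**The concern.** Safety of long-term losmapimod is the primary endpoint of the OLE (SAP 3.2.1). A worst-value table answers a simple question: how far out of range did subjects go on the drug? For those randomized to losmapimod, the planned tables answer it. For former placebo subjects they answer a different question, namely how far out of range the subject went on either treatment, measured from a baseline taken 24 or 48 weeks before the first losmapimod dose. A shift to high or low in those columns cannot be attributed to losmapimod from the table.

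The AE question is one of period. An event that began in the OLE but has an incomplete onset date may be imputed to a date before the OLE. For a former placebo subject, a losmapimod event would then be shown under placebo. An AE that begins on placebo and worsens on losmapimod also has no rule placing it in the OLE tables.

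**Working it through.** The plan states no figure of its own here, so the check is a count of visits and a trace of the date rules.

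**1. Scheduled chemistry panels** (hematology has the same schedule). Protocol Table 2 has post-baseline panels at Weeks 4, 12, 16, 24, 36 and 48, which is 6. The OLE visits run every 12 weeks from Week 60 to Week 216 (SAP Table 4-1): (216 − 60)/12 + 1 = 14. The first OLE dose is the day after the Week 48 visit, or after Week 24 for early entrants (SAP 3.1), so the entry visit itself belongs to placebo.

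| Placebo entrants | Panels on placebo | All post-baseline panels | Share |
|---|---|---|---|
| Week 48, to Week 216 | 6 | 6 + 14 = 20 | 30% |
| Week 24, to Week 216 | 4 | 4 + 2 + 14 = 20 | 20% |
| Week 48, to Week 144 | 6 | 6 + 8 = 14 | 43% |

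Missed visits change these shares. If a Week-48 entrant missed Weeks 16 and 24, the first row becomes 4/(4 + 14) = 22%. Unscheduled, early-termination and follow-up samples are not counted.

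**2. ECG, only if the maximum-QTcF table pools both periods.** Post-baseline ECGs are at Weeks 4 and 48, then at each OLE visit. This gives 2/(2 + 14) = 12.5% for Week-48 placebo entrants and 1/(1 + 1 + 14) = 6% for Week-24 entrants.

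**3. AE date rules.** Take assumed dates: first study drug 12 Nov 2019, first OLE dose 336 days later on 13 Oct 2020, true onset 20 Oct 2020. SAP 9.1 gives 1 Oct 2020 (day missing), 20 Jan 2020 (month missing) or 1 Jan 2020 (both missing). All three fall before the OLE. For an onset after the first dose, no branch yields a date later than the true one, so movement is out of the OLE only.

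**4. Would re-anchoring to the first OLE dose help?** Assumptions: first doses in several windows between June 2019 and 9 Apr 2020 (to 24 Oct 2019 for Week-24 entrants), uniform onset through Week 216, and an equal daily AE rate in both periods. The re-anchored figures are upper bounds, because they assume that no AE ended before the OLE began. Share misplaced × days in the period gives day-equivalents misplaced:

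| Entrants, missing part | SAP 9.1 dates: OLE onsets moved out | Re-anchored: RCT onsets moved in (upper bound) |
|---|---|---|
| Week 48, day | 1.22–1.29% × 1,176 = 14–15 | 4.3–4.4% × 336 = 14–15 |
| Week 48, day and month | 10.7–14.3% × 1,176 = 126–168 | 58.1–70.4% × 336 = 195–237 |
| Week 24, day | 1.04–1.06% × 1,344 = 14 | 8.8–8.9% × 168 = 15 |
| Week 24, day and month | 16.5–23.0% × 1,344 = 222–309 | 33.8–51.9% × 168 = 57–87 |

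On these bounds, re-anchoring breaks even when only the day is missing. For year-only dates it can be worse in Week-48 entrants. It does better in Week-24 entrants, but only 12 subjects rolled over at Week 24 (protocol 3.1.1).

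**The case against.** **Laboratory tables.** A reader might infer that the plan hides which treatment produced a worst value. It does not. SAP 4 lists all data by treatment sequence and analysis period, SAP 4.4 adds study day relative to first losmapimod where appropriate, and hematology, chemistry and ECG listings are planned. With 80 subjects enrolled, any extreme value can be traced. Change from baseline at OLE visits is computed from both baselines, and the liver and DILI tables are by visit. All of this stands. What remains is a gap in the summary layout of the two shift tables.

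The shares above might also be read as the chance that a worst value came from placebo. That would need exchangeable readings and full attendance, and protocol 3.2.2 reports many missed Week 16 and Week 24 visits.

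**QTcF.** It is tempting to say that the maximum-QTcF table (14.3.5.3.3) has the same defect. SAP 9.5 refers to on-treatment values by treatment group, defines neither term, and the shells are in a separate document. Only the missing definitions can be criticized.

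**Adverse events.** A reader might infer that OLE AE counts will be understated. SAP 9.1 imputes dates to decide inclusion in the TEAE tables; it does not say that the same dates allocate the period. Drug treatment is recorded with each AE (protocol 6.2.1.5), and AEs are elicited at every visit (6.2.1.4), so year-only onsets should be uncommon. The documents give no count of partial dates, and the effect may be nil. The missing allocation rule stands; a claim of bias does not.

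**Conclusion.** Minor, but real. In the placebo/losmapimod columns of Tables 14.3.4.1.2 and 14.3.4.2.2 a worst value may be a placebo value, and no planned summary table isolates losmapimod. By schedule, placebo supplies 30% (Week-48 entrants) or 20% (Week-24 entrants) of post-baseline panels through Week 216. This rests on full attendance and describes exposure of the table to the problem, not its effect on any result. The losmapimod/losmapimod columns are unaffected.

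The AE point is a request for clarification. SAP 9.1 anchors every partial onset on the first study drug dose and states no rule for allocating such events, or those that worsen after the switch, to a period. If the imputed dates are used for the split, the error runs only out of the OLE. TEAE status and the cumulative AE tables do not change. Its size cannot be computed from the documents.

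**What to change.** 1. Keep the existing shift tables and add hematology and chemistry versions restricted to the losmapimod exposure period of SAP 4.1. Take baseline as the last value before the first losmapimod dose; for placebo/losmapimod subjects that is the OLE baseline of SAP 4.4.
2. Define *on-treatment* and *treatment group* in SAP 9.5. If the shells pool both periods, add the same restricted version of Table 14.3.5.3.3.
3. State in SAP 9.1 how AEs with partial or missing onset dates, and AEs that begin on placebo and worsen on losmapimod, are allocated to the two sets of tables. Use the end date, the drug treatment recorded at the event and the visit at which it was recorded. Report how many events have imputed dates, and show OLE counts with and without year-only dates. Do not present re-anchoring to the first OLE dose as removing error, since it can move a similar or larger number of RCT onsets into the OLE.

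The cost is SAP text and a few more tables; the period and both baselines are already defined. The later baseline can move shifts in either direction, so both versions should be shown. Severity changes are documented under protocol 6.2.1.8, but intermittent AEs need no onset date per episode, so worsening may not be datable for those.
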